4. ANALYSIS SETS (POPULATIONS FOR ANALYSIS)

Data for all participants will be assessed to determine if participants meet the criteria for inclusion in each analysis population prior to unblinding and releasing the database and classifications will be documented per standard operating procedures.

Participant Analysis Set	Description
Enrolled/Randomly assigned to study intervention	"Enrolled" means a participant's, or their legally authorized representative's, agreement to participate in a clinical study following completion of the informed consent process. Potential participants who are screened for the purpose of determining eligibility for the study, but do not participate in the study, are not considered enrolled, unless otherwise specified by the protocol.
Safety	All participants randomly assigned to study intervention and who take at least 1 dose of study intervention. Participants will be analyzed according to the product they actually received.
PK concentration	All participants randomly assigned to study intervention who received a dose of PF-07038124 and in whom at least 1 plasma sample concentration value is reported.
PK parameter	All participants randomly assigned to study intervention who received a dose of PF-07038124 and who have at least 1 of the PK parameters of interest calculated.

5. GENERAL METHODOLOGY AND CONVENTIONS

This is a double-blind study. Final analysis will follow the official database release.

5.1. Hypotheses and Decision Rules

There are no statistical hypotheses or decision rules.

5.2. General Methods

5.2.1. Analyses for Binary Endpoints

Binary endpoints will be summarized by treatment and visit (if appropriate) with number and percentage of participants in each category, if not otherwise specified.

5.2.2. Analyses for Continuous Endpoints

Continuous endpoints will be summarized by treatment and visit (if appropriate) using descriptive statistics, including n, arithmetic mean, median, standard deviation (SD), minimum and maximum will be used to summarize the endpoints, if not otherwise specified.

5.2.3. Analyses for Categorical Endpoints

Categorical endpoints will be summarized by treatment and visit (if appropriate) with number and percent of participants in the treatment group within each category, if not otherwise specified.

5.2.4. Analyses for Time-to-Event Endpoints

There are no time-to-event endpoints in this study.

5.3. Methods to Manage Missing Data

5.3.1. Standard Safety Data

For the analysis of standard safety data (i.e., all safety data except local skin irritation), the sponsor data standard rules for imputation will be applied.

5.3.2. Skin Irritation Assessment

Missing values will not be imputed.

5.3.3. Pharmacokinetic Data

Concentration Below the Limit of Quantification

In all data presentations (except listings), concentrations below the limit of quantification (BLQ) will be set to zero. (In listings BLQ values will be reported as “<LLQ”, where LLQ will be replaced with the value for the lower limit of quantification.)

Deviations, Missing Concentrations and Anomalous Values

In summary tables, plots of mean profiles and plots of median profiles, summary statistics will be calculated setting concentrations to missing if one of the following cases is true:

1. A concentration has been collected as ND (i.e., not done) or NS (i.e., no sample);
2. A deviation in sampling time is of sufficient concern or a concentration has been flagged anomalous by the pharmacokineticist.

Note that summary statistics will not be presented at a particular time point if more than 50% (>50%) of the data are missing.

Pharmacokinetic Parameters

Actual PK sampling times will be used in the derivation of PK parameters.

If a PK parameter cannot be derived from a participant's concentration data, the parameter will be coded as NC (i.e., not calculated). (Note that NC values will not be generated beyond the day that a participant discontinues.)

In summary tables, statistics will be calculated by setting NC values to missing; and statistics will be presented for a particular dose with ≥ 3 evaluable measurements.

If an individual participant has a known biased estimate of a PK parameter (due for example to an unexpected event), this will be footnoted in summary tables and will not be included in the calculation of summary statistics.

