#### 2.2.4.2. Clinical Pharmacokinetics

Following multiple topical administration of PF-07038124 following 10 days of dosing, the majority of concentrations on Day 1 were BLQ and a limited number of participants had valid parameter values. PF-07038124 was absorbed rapidly followed by a biexponential decline, with  $C_{max}$  achieved at a median  $T_{max}$  of 4 to 6 hours for treatments where median values could be reported. Individual values ranged between 2 to 8 hours for all treatments. For the 0.01% QD (Cohort 1), 0.01% BID (Cohort 2), and 0.03% QD (Cohort 3) cohorts, geometric mean  $C_{av}$  on Day 10 was 37.43, 88.82, and 187.1 pg/mL, respectively in Table 2. Individual  $t_{1/2}$  on Day 10 ranged from 8.49 to 17.4 hours for treatments where  $t_{1/2}$  could be reported. Geometric mean CL/F values ranged from 400.5 to 668.4 L/hr for treatments where mean values could be reported. In general, plasma PF-07038124 exposure appeared to increase in a greater than dose-proportional manner for  $AUC_{tau}$ , and an approximate dose-proportional manner for  $C_{max}$ .

Individual accumulation ratios were 3.59 for  $AUC_{tau}$  ( $R_{ac}$ ) and ranged from 2.69 to 35.8 for  $C_{max}$  ( $R_{ac,Cmax}$ ), respectively on Day 10. The PF-07038124 median trough plasma concentrations approached steady state following 10 days of dosing.

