**Table 2. Descriptive Summary of Day 10 Plasma PF-07038124 PK Parameters, C3941001**

Day 10 PK Parameter a,b	Part B Cohort 1 (2000 cm  ) PF-07038124 0.01% QD (N=6)	Part B Cohort 2 (2000 cm  ) PF-07038124 0.01% BID (N=6)	Part B Cohort 3 (2000 cm  ) PF-07038124 0.03% QD (N=6)	Part B Cohort 4 (4000 cm  ) PF-07038124 0.01% QD (N=2)
$AUC_{tau}$ (pg.hr/mL)	897.2 (44)	1068 (44)	4491 (57)	N/A
$C_{av}$ (pg/mL)	37.43 (44)	88.82 (44)	187.1 (57)	N/A
$C_{max}$ (pg/mL)	52.78 (59)	104.7 (49)	264.7 (70)	48.8, 96.0 b

$C_{\text{trough}}$ (pg/mL)	26.95 (48)	87.73 (47)	147.4 (66)	41.8, 86.2 b
--------------------------------	------------	------------	------------	-------------------------

- a. Geometric mean (geometric %coefficient of variation)
- b. Individual values are listed when there are less than 3 evaluable measurements.

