## 9.2. Sample Size Determination

A sample size of 12 participants (4 PF-07038124: 2 vehicle per cohort) has been selected empirically to permit adequate characterization of safety, tolerability, skin irritation potential, and PK at each dose level in Japanese healthy participants. Participants who discontinue prior to completion of the study for non-safety related reasons may be replaced, at the discretion of the PI and Sponsor.

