#### **9.4.3. Secondary Endpoint(s)**

##### **9.4.3.1. Pharmacokinetic Analyses of PF-07038124**

PK parameters (AUCtau, and Cmax) for PF-07038124, following multiple-dose topical administration, will be derived from the plasma concentration-time profiles using noncompartmental methods, as data permit.

The PK parameters to be assessed in this study, their definition, and method of determination are listed in [Table 5](#). Actual PK sampling times will be used in the derivation of PK parameters.

No formal inferential statistics will be applied to the PK data.

The plasma PK parameters in [Table 5](#) will be summarized descriptively by treatment group in accordance with Pfizer data standards, as data permit. The plot will include individual

participant values and the geometric means for each dose. These plots will be used to help understand the relationship between the PK parameters and dose.

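### Can the Day 1 Cmax summary rest on the three highest of four participants without the table saying why?

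*SAP*

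**What the plan says.** SAP 5.3.3 treats concentrations and parameters separately.

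- **Concentrations.** "In all data presentations (except listings), concentrations below the limit of quantification (BLQ) will be set to zero". Samples not taken, and values flagged as anomalous, are set to missing. Listings show BLQ results as '<LLQ' with the limit filled in.
- **Parameters.** When no value can be obtained from someone's "concentration data, the parameter will be coded as NC (i.e., not calculated"). Then: "In summary tables, statistics will be calculated by setting NC values to missing; and statistics will be presented for a particular dose with" three or more evaluable values. A footnote is required only for an estimate known to be biased, which is also left out of the statistics.

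SAP 6.2.1 summarises AUCtau and Cmax by day and treatment group. Its Table 3 asks for n, arithmetic mean, median, SD, range, %CV, geometric mean and geometric %CV. It also requires listings, and plots of individual values for each day.

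Protocol 9.4.3.1 says of the parameters that "their definition, and method of determination are listed in" Table 5, and Table 5 is redacted. On size, Protocol 9.2 says: "A sample size of 12 participants (4 PF-07038124: 2 vehicle per cohort) has been selected empirically". On the first study, C3941001, Protocol 2.2.4.2 reports that "the majority of concentrations on Day 1 were BLQ and a limited number of participants had valid parameter values", and that individual Cmax accumulation ratios "ranged from 2.69 to 35.8 for" Day 10 against Day 1.

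**The concern.** The single code NC carries no reason. Take a cohort of four in which one participant has every Day 1 sample BLQ. That person's Cmax is not unknown: it is the lowest of the four. If it is coded NC, it is treated like a value lost at random. Three values remain, the summary is shown, and it describes the three highest. The table would show n = 3 but neither the cause nor the direction.

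The situation is foreseeable, because C3941001 had mostly BLQ concentrations on Day 1 and included the same 0.01% once-daily regimen. The accumulation ratios show that some Day 1 Cmax values were calculable, so summaries on part of a cohort are plausible. Because one calculated parameter is enough to enter the PK parameter set, a Day 1 row on three people could stand beside a Day 10 row on four. A reader could then take Day 1 Cmax to be higher and less variable than it was, and so understate accumulation.

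The other coding, Cmax = 0, also has a cost: the planned geometric mean becomes zero and the geometric %CV undefined.

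**Working it through.** **The plan's own figure.** 2 cohorts × (4 active + 2 vehicle) = 12, as stated in Protocol 9.2. There is no power calculation to rebuild.

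**Inputs.**

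- Active participants per cohort: 4 (Protocol 9.2).
- Minimum for a summary: 3 evaluable values (SAP 5.3.3).
- Geometric CV of Cmax: 49%, 59% and 70%. These are Day 10 values from Protocol Table 2; 59% is for 0.01% once daily on 2000 cm². Using them for Day 1 is an assumption.
- q, the share of participants with a quantifiable Day 1 Cmax: not given. The range 0.9, 0.75, 0.5 and 0.3 is assumed.
- Limit of quantification: not given.

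**Reading A: all-BLQ is coded NC.** Take Cmax as lognormal with σ = √ln(1 + CV²), which gives 0.464, 0.547 and 0.631. A participant is dropped when Cmax falls below the limit.

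- Exactly one of four dropped: 4q³(1 − q)
- No summary (two or more dropped): 1 − q⁴ − 4q³(1 − q)
- Share of displayed summaries that rest on three: 4(1 − q) / [q + 4(1 − q)]
- Average ratio of the geometric mean of the three to that of the same four: exp{σ[φ(c)/q + φ(c)/(1 − q)]/4}, where c is the normal quantile of 1 − q

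Worked case, CV 59% and q = 0.5: c = 0 and φ(c) = 0.399. The bracket is 0.798 + 0.798 = 1.596, and one quarter of it is 0.399. The ratio is exp(0.547 × 0.399) = 1.244.

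| q | One of four dropped | No summary | Displayed summaries on three | Ratio, CV 49% | CV 59% | CV 70% |
|---|---|---|---|---|---|---|
| 0.9 | 29% | 5% | 31% | 1.254 | 1.305 | 1.360 |
| 0.75 | 42% | 26% | 57% | 1.217 | 1.261 | 1.307 |
| 0.5 | 25% | 69% | 80% | 1.203 | 1.244 | 1.287 |
| 0.3 | 8% | 92% | 90% | 1.212 | 1.254 | 1.299 |

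The displayed median would be 7-19% higher than that of the same four. At CV 59% the typical geometric CV would be 22-40% instead of 51-70%. For scale, one standard error of a geometric mean of four is a factor exp(σ/2) = 1.26, 1.31 and 1.37 for the three CVs, so the average shift is at most about one standard error.

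**Reading B: all-BLQ gives Cmax = 0.** Then n = 4 and nobody is left out. The median, range and arithmetic mean are shown, and the minimum of 0 shows what happened. With one of four at zero, the median is the mean of the second and third values, so it is unaffected. Only the geometric statistics fail, and they fail visibly.

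**Which reading applies?** The visible text does not settle it. NC is for a parameter that cannot be derived; a maximum over values set to zero can be derived, and equals zero. Finite accumulation ratios do not decide it either, since a Day 1 value of zero and one of NC both yield no ratio.

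**Are two causes really merged for Cmax?** Hardly. The Day 1 schedule has eight samples, seven of them post-dose. A missed sample seldom prevents a Cmax, and an estimate known to be biased is footnoted. Mixed causes matter more for AUCtau, where the rank of an NC value is unknown and no direction can be claimed.

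**Would added wording help?** Ranking the participant as '<LLQ' gives, with one of four BLQ, the same median as Reading B. With two of four BLQ, that median is not a determinable number; this has probability 6q²(1 − q)², or 21%, 38% and 26% at q = 0.75, 0.5 and 0.3. A geometric mean still has to be taken over quantifiable values, so the 20-36% shift would remain under a footnote.

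**The case for a change.** The strongest case for acting is that both codings leave a weak Day 1 Cmax summary, so the point does not depend on what the redacted Table 5 says. The situation was visible in the first study. A stated rule, a count of all-BLQ participants and a footnote would cost a few lines and lose no statistic now planned. When few participants are quantifiable, most of the summaries that do appear would rest on the three highest values, and their apparent spread would be roughly halved.

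Much of this stands. No visible text gives the rule, no count or reason for NC is required, and the arithmetic is right under its assumptions.

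It does not carry the case for three reasons. First, the selective summary arises only under a coding that the SAP does not state, and text lost to redaction cannot be counted as missing. Second, the report already lets a reader trace the cause, through n, the parameter listing, the individual plots by day and the '<LLQ' entries. In concentration summaries, where BLQ is zero, the participant is not dropped. Third, the evidence from the first study points to a low quantifiable fraction, where the usual result is no summary at all (69% of cohorts at q = 0.5 and 92% at q = 0.3). In that event the sponsor's practice in Protocol Table 2 was sound: "Individual values are listed when there are less than 3 evaluable measurements".

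**Conclusion.** No change to the plan follows. The visible text leaves open whether an all-BLQ Day 1 Cmax is 0 or NC, but this is missing detail of a kind that PK analysts settle routinely, and Table 5 may already settle it. It does not show that a stated rule gives a wrong result.

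If the coding is NC and exactly one of four is dropped, the Day 1 geometric mean is on average 20-36% above that of the same four, and its spread is too narrow. That size rests on a lognormal Cmax, on Day 10 CVs borrowed for Day 1, and on an assumed range for the quantifiable fraction. If the coding is 0, the shift does not arise and only the geometric statistics are lost.

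Either way, the quantity is a descriptive secondary endpoint that the plan reports only as far as the data allow. No hypothesis or sample size depends on it. Protocol 4.3 chose Cohort 1 for PK comparison with the first study, and the parameters tabulated from that study in Protocol Table 2 are for Day 10 only. A reader of the Day 1 row should look at n and the individual values before the geometric mean, and the planned outputs make that possible.

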6. ANALYSES AND SUMMARIES

All analyses described below will be conducted by treatment and cohort. In addition, data from vehicle in Cohort 1 and Cohort 2 will be pooled.

6.1. Primary Endpoint(s)

The primary endpoints of this study are the standard safety endpoints and local skin irritation presented in the Section 3.1. A set of summary tables split by cohort and treatment group (including pooled vehicle group) will be produced to evaluate potential risk associated with the safety and toleration of administering PF-07038124.

No formal analyses are planned safety data. The safety endpoints will be listed and summarized in accordance with the sponsor reporting standards, where the resulting data presentations will consist of participants from the safety analysis set.

6.1.1. Adverse Events

Adverse events will be listed and summarized in accordance with the sponsor reporting standards.

6.1.2. Laboratory Data

Laboratory data will be listed and summarized in accordance with the sponsor reporting standards. Baseline is as defined in Section 3.5.2.

6.1.3. Vital Signs Data

Absolute values and changes from baseline in supine systolic and diastolic blood pressure and pulse rate will be summarized by cohort, treatment group and postdose timepoints, according to the sponsor reporting standards. Tables will be paged by parameter. Baseline is as defined in Section 3.5.3.

Mean changes from baseline for systolic and diastolic blood pressure and pulse rate will be plotted against time postdose. On each plot there will be 1 line for each treatment. Data from all cohorts will be plotted on the same figure using separate lines for the 2 vehicles. Corresponding individual plots of change from baseline will also be produced for each cohort and treatment.

Maximum absolute values and changes from baseline for vital signs will also be summarized descriptively by treatment and cohort using categories as defined in [Appendix 1](#). Numbers and percentages of participants meeting categorical criteria will be provided. All planned and unplanned postdose timepoints will be counted in these categorical summaries. All values meeting the criteria of potential clinical concern will be listed.

If necessary, maximum increases or decreases in vital signs may be summarized in addition to the above.

6.1.4. Electrocardiograms

Absolute values and changes from baseline in QT, heart rate, QTcF, PR and QRS will be summarized by cohort, treatment group and postdose timepoints. Baseline is as defined in Section [3.5.4](#). Tables will be paged by parameter.

Mean changes from baseline in QT, heart rate, QTcF, PR and QRS will be plotted against time postdose. On each plot there will be 1 line for each treatment. Data from all cohorts will be plotted on the same figure using separate lines for the 2 vehicles. Corresponding individual plots of change from baseline will also be produced for each cohort and treatment.

Changes from baseline in QTcF will also be plotted separately against PF-07038124 concentrations. This will be a scatter plot for all observations where QTcF and PF-07038124 concentration are recorded. Vehicle data will also be included (with drug concentration set to zero). Data from all cohorts will be plotted on the same figure. Different symbols will be used for each treatment.

The number (%) of participants with maximum postdose QTcF values and maximum increases from baseline in the following categories will be tabulated by cohort and treatment group:

Safety QTcF Assessment

Degree of Prolongation	Mild (msec)	Moderate (msec)	Severe (msec)
Absolute value	>450-480	>480-500	>500
Increase from baseline		30-60	>60

In addition, the number of participants with uncorrected QT values >500 msec will be summarized.

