1. VERSION HISTORY

Table 1. Summary of Changes

Version/ Date	Associated Protocol Amendment	Rationale	Specific Changes
1 10 Mar 2021	Original 08 Jan 2021	N/A	N/A
2 21 Sep 2021	Amendment 1 12 Mar 2021	Clarification and addition of analyses	
 Added plots of vital signs data (section 6.1.3) Added plots of ECG data (section 6.1.4) Clarified analyses of skin irritation assessment (section 6.1.5) Added categorical class for QT of potential clinical concern to align with section 6.1.4 (appendix 1)

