Appendix 1. Categorical Classes for ECG and Vital Signs of Potential Clinical Concern

CATEGORIES FOR QTcF

QTcF (ms)	450≤ max. <480	480≤ max.<500	max. ≥500
QTcF (ms) increase from baseline	30≤ max. <60	max. ≥60	

CATEGORIES FOR QT

QT (ms)	max. ≥500		
---------	-----------	--	--

CATEGORIES FOR PR AND QRS

PR (ms)	max. ≥300	
PR (ms) increase from baseline	Baseline >200 and max. ≥25% increase	Baseline ≤200 and max. ≥50% increase
QRS (ms)	max. ≥140	
QRS (ms) increase from baseline	≥50% increase	

CATEGORIES FOR VITAL SIGNS

Systolic BP (mm Hg)	min. <90	
Systolic BP (mm Hg) change from baseline	max. decrease ≥30	max. increase ≥30
Diastolic BP (mm Hg)	min. <50	
Diastolic BP (mm Hg) change from baseline	max. decrease ≥20	max. increase ≥20
Supine pulse rate (bpm)	min. <40	max. >120
Standing pulse rate (bpm)	min. <40	max. >140

Measurements that fulfill these criteria are to be listed in report.

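### Does it matter that SAP 6.1.4 and SAP Appendix 1 put exact QTcF and QT limits on different sides of the category boundary?

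*SAP*

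**What the plan says.** SAP 6.1.4 contains its own table of QTcF categories. Absolute values are classed as >450-480, >480-500 and >500 msec, and increases from baseline as 30-60 and >60 msec. It then adds for QT: "In addition, the number of participants with uncorrected QT values >500 msec will be summarized". Protocol 9.4.2.1 has the same categories and the same QT rule.

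SAP Appendix 1 sets out categorical classes for ECG and vital signs. Its QTcF classes run from 450 up to but not including 480, from 480 up to but not including 500, and from 500 upward. Its increase classes run from 30 up to but not including 60, and from 60 upward. Its QT class starts at 500 inclusive. It ends: "Measurements that fulfill these criteria are to be listed in report".

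The SAP version history for version 2 records: "Added categorical class for QT of potential clinical concern to align with section 6.1.4 (appendix 1".

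SAP 6.1.3 (vital signs) refers to Appendix 1 for its categories. SAP 6.1.4 (ECG) does not.

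**The concern.** Clinically significant ECG change is one component of the primary endpoint (SAP 3.1), and one SAP holds two sets of cut-points for the same ECG measurements. A programmer working from 6.1.4 and another working from Appendix 1 would class some values differently. A value could then appear in the listing of potential clinical concern with no matching count in the table.

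The version history adds to the impression of a slip: a QT row was added so that the appendix would agree with 6.1.4, yet one place has >500 and the other ≥500. Cells are very small (4 active and 2 vehicle participants per cohort, Protocol 9.2), so one participant on a boundary changes a percentage visibly.

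**Working it through.** The plan gives no figure to reproduce here, so the check compares the two rule sets and then sizes the discrepancy.

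**Step 1. Apply both rules to every value.** The inputs are the categories in SAP 6.1.4 and in SAP Appendix 1. The range 30-60 is read as including 30. On a 0.1 msec grid (QTcF and QT from 300 to 599.9, QTcF change from -100 to 119.9) the rules differ at five values only:

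| Measure | Exact value (msec) | SAP 6.1.4 | SAP Appendix 1 | Consequence |
|---|---|---|---|---|
| QTcF | 450 | no category | lowest class | listed, not counted |
| QTcF | 480 | mild | middle class | class differs |
| QTcF | 500 | moderate | top class | class differs |
| QTcF increase | 60 | moderate | top class | class differs |
| QT | 500 | not counted | counted | listed, not counted |

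An increase of exactly 30 agrees. If 30-60 were read as excluding 30, that would be a sixth value, also of the listed-but-not-counted kind.

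**Step 2. Check which way the mismatch runs.**
- QTcF counted in 6.1.4: >450. Listed under Appendix 1: ≥450.
- Increase counted: ≥30. Listed: ≥30.
- QT counted: >500. Listed: ≥500.

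Each counted set lies inside the listed set. No participant counted in the table can be missing from the listing. The listing can only hold extra values, at QTcF 450 and QT 500.

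**Step 3. Effect on a cell.** One boundary participant moves a percentage by 1/4 = 25 points in an active group, 1/2 = 50 points in a single-cohort vehicle group, and 1/4 = 25 points in the pooled vehicle group.

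**Step 4. How likely is a boundary value?** The documents give no ECG distribution, so these are assumptions. For a participant maximum with mean m and SD s, recorded as an integer:

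p = Φ((x + 0.5 − m)/s) − Φ((x − 0.5 − m)/s), and the chance of at least one in 12 is 1 − (1 − p)^12.

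For QTcF 450 with Normal(415, 20): p = Φ(1.775) − Φ(1.725) = 0.00432, and 1 − 0.99568^12 = 5.06%.

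| Exact maximum | Assumed range | Chance of at least 1 in 12 |
|---|---|---|
| QTcF 450 | Normal(405, 15) to Normal(425, 20) | 0.35% to 10.4% |
| QTcF 480 | same | 0.0001% to 0.54% |
| QTcF 500 | same | up to 0.02% |
| Increase 60 | Normal(10, 10) to Normal(15, 15) | 0.0002% to 0.35% |
| QT 500 | Normal(410, 25) to Normal(430, 30) | 0.03% to 1.0% |

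If QTcF is derived by the Fridericia formula, as SAP 3.5.4 allows when it is not supplied, and is left unrounded, an exact hit becomes rarer still.

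**The case for a change.** The strongest case for a change is that both sets are current and legible, and the SAP does not say outright which one drives the ECG table. QTcF 450 is also attainable: the baseline ECG exclusion in Protocol 5.2 gives QTcF above 450 as its example, so a participant at exactly 450 is not excluded on that ground. Editing three appendix rows before unblinding would cost almost nothing.

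The textual difference stands. The rest carries less weight:

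- **Which rule drives what.** The natural reading gives each output one rule. Section 6.1.4 prints its table in full and does not point to the appendix, while the appendix's own instruction concerns a listing. Analysts would take the table from 6.1.4, which is also the protocol's table.
- **Reconciliation.** At QTcF 480, QTcF 500 and an increase of 60, the value is listed and the participant is counted, so the reader can match them. Only QTcF 450 and QT 500 leave an unmatched listing entry, and its value shows why.
- **Version history.** The entry is satisfied by the addition of a QT row, since 6.1.4 reports QT. It does not show that the inequality signs were meant to match.
- **Direction of any edit.** Moving the appendix to the 6.1.4 limits would remove two values from a listing of potential clinical concern. Moving 6.1.4 to the appendix limits would depart from Protocol 9.4.2.1. The signs used elsewhere do not settle it: Protocol 8.2.3 uses ≥500 and ≥60, Protocol 7.1 uses >500 and >60, and Protocol Appendix 7 mixes the two. Those limits serve clinical purposes, and nothing here bears on them.
- **Link to the primary endpoint.** Neither document says that these bins define a clinically significant ECG change. Protocol Appendix 3 leaves that to the investigator's judgment.

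**Conclusion.** No change follows. This is a minor inconsistency in reporting limits, and removing it would bring no gain. Followed as written, the ECG table agrees with the protocol, the listing contains every counted case, and the only possible mismatch is an extra listing entry at a QTcF of exactly 450 or a QT of exactly 500.

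There is no hypothesis, decision rule or sample-size calculation for it to affect (SAP 5.1, Protocol 9.1 and 9.2). SAP 6.1 also has the safety endpoints both listed and summarized, and SAP 6.1.4 adds individual plots of change from baseline, so a boundary case among about 12 participants would be seen whichever bin it fell in.

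The conclusion rests on three assumptions: the table and QT count follow 6.1.4 while the listing follows Appendix 1; 30-60 includes 30; and the probabilities come from assumed normal distributions with integer readings. The first matters most. If the table were programmed from Appendix 1 instead, one participant could change class at one of the five values, but the ECG findings would still be descriptive and the individual values still visible.
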